**Efficacy measures:**

PGA, BSA, NL Lesion Score, Pruritus NRS, Skindex-16

**Primary Outcome Measures:**

To determine the efficacy of ruxolitinib cream as measured by the change in NL score (0-12) of the index treatment lesions (weeks 0 and 12).

**Secondary Outcome Measures:**

To determine the efficacy of ruxolitinib and the duration of response after discontinuation as measured by the change in Pruritus NRS, (week 0 to week 4, week 0 to week 8, week 0 to week 12, week 0 to 16, weeks 4 to 8, weeks 8 to 12, weeks 12 to 16), Change in Skindex-16 (week 0 to week 4, week 0 to week 8, week 0 to week 12, week 0 to 16, weeks 4 to 8, weeks 8 to 12, weeks 12 to 16), Change in Physician Global Assessment (PGA) (week 0 to week 4, week 0 to week 8, week 0 to week 12, week 0 to 16, weeks 4 to 8, weeks 8 to 12, weeks 12 to 16), Change in affected BSA% (week 0 to week 4, week 0 to week 8, week 0 to week 12, week 0 to 16, weeks 4

to 8, weeks 8 to 12, weeks 12 to 16), Change in NL Lesion Score (week 0 to week 4, week 0 to week 8, week 0 to week 12, week 0 to 16, weeks 4 to 8, weeks 8 to 12, weeks 12 to 16). Change in lesional volume (week 0 to week 4, week 0 to week 8, week 0 to week 12, week 0 to 16, weeks 4 to 8, weeks 8 to 12, weeks 12 to 16).

#### Exploratory Outcome Measures:

To predict responses and examine the pharmacodynamics of treatment through the identification of unique biomarkers and transcriptomic changes of NL at week 0 and utilizing RNA sequencing on responsive and non-responsive tissue at week 12 if data allows to correlate these biomarkers with measures of global response: NL Lesion Score, PGA, and BSA.

### **3.2 Number of Subjects**

12 subjects will be enrolled in this study.

#### Tables:

**Table-1: Prohibited treatment**

Prohibited treatments†,‡	Washout period (before initiation of trial medication)
Any concomitant oral or topical JAK inhibitor	Prohibited
Any biologic drug for NL *	3 months or 5x half-life (whichever is longer)
Immunomodulation treatments for NL § [e.g., methotrexate, cyclosporine A, corticosteroids (oral, i.v., intramuscular, s.c., intra-articular, transdermal), mycophenolate mofetil, azathioprine ]	4 weeks
Topical treatment that is likely to impact signs and symptoms of NL (e.g., pimecrolimus, tacrolimus) if applied onto NL lesions	2 weeks
Non-immunosuppressive, anti-inflammatory agents (tetracycline antibiotics & niacinamide)	2 weeks

**Prohibited regimen of Topical Corticosteroids (TCS)**

TCS on any location on body (including face, scalp and/or genitoanal area)      2 weeks

---

\*Treatments with biologics for other indications permitted at 3 months or 5x half-life (whichever is longer)

† If the prohibited treatment is being used during the study for any indication, the subject must discontinue use of the prohibited treatment if he/she wishes to continue in the study.

‡ In case of undue safety risk for the subject, the subject should discontinue study treatment at the discretion of the investigator/qualified site staff. If the subject received a live virus vaccination during the study, the subject must discontinue study treatment.

§Inhalative CS with only a topical effect (e.g., to treat asthma) are not considered “systemic immunomodulation treatments” and are therefore acceptable as co-medication.

Immunosuppressive medication for conditions other than NL will be allowed.

**Table-2: Screening and Visits (+/- 3 day window)**

	Screening	Day 0	Week 1	Week 2	Week 3	Week 4	Week 8	Week 12	Week 16
Ruxolitinib*		X	X	X	X	X	X		
Physical Exam	X	X	X	X	X	X	X	X	X
Adverse Event Assessment		X	X	X	X	X	X	X	X
Chest X-ray	X								
Assessments: PGA, BSA, lesional number, NL Lesion, Skindex-16, Pruritus NRS		X	X	X	X	X	X	X	X
Photographer		X	X	X	X	X	X	X	X
Skin Biopsy (tissue/serum bank)		X				X			
Urine Pregnancy Test	X								
Venipuncture	X	X	X	X	X	X	X	X	X
Biomarker/RNAseq blood (tissue/serum bank)		X		X		X	X	X	
CMP	X		X	X	X	X	X	X	X
CBC	X		X	X	X	X	X	X	X
Quantiferon Gold	X								
Hepatitis B	X								
Hepatitis C	X								
HIV	X								
Coccidioidomycosis	X								

\*Patients will receive 1.5% ruxolitinib cream tubes to apply cream at home BID inbetween visits to be applied from Day 0 through Week 12. Patients will not receive 1.5% ruxolitinib cream at Week 12 visit as this begins their follow up period.

### **3.4 Primary Study Endpoints**

Change in NL score (0-12) of the index treatment lesions (weeks 0 and 12).

### **3.5 Secondary Study Endpoints**

Change in Pruritus NRS, (week 0 to week 4, week 0 to week 8, week 0 to week 12, week 0 to 16, weeks 4 to 8, weeks 8 to 12, weeks 12 to 16), Change in Skindex-16 (week 0 to week 4, week 0 to week 8, week 0 to week 12, week 0 to 16, weeks 4 to 8, weeks 8 to 12, weeks 12 to 16), Change in Physician Global Assessment (PGA) (week 0 to week 4, week 0 to week 8, week 0 to week 12, week 0 to 16, weeks 4 to 8, weeks 8 to 12, weeks 12 to 16), Change in BSA (week 0 to week 4, week 0 to week 8, week 0 to week 12, week 0 to 16, weeks 4 to 8, weeks 8 to 12, weeks 12 to 16), Change in NL Lesion Score (week 0 to week 4, week 0 to week 8, week 0 to week 12, week 0 to 16, weeks 4 to 8, weeks 8 to 12, weeks 12 to 16). Change in lesional volume (week 0 to week 4, week 0 to week 8, week 0 to week 12, week 0 to 16, weeks 4 to 8, weeks 8 to 12, weeks 12 to 16).

### **3.6 Primary Safety Endpoints**

A thorough baseline screening will be followed for all patients and is outlined in Table-2. A detailed list of the methods in which baseline screening will be performed is outlined in Supplemental 2. All blood draws and safety assessments must be performed prior to study treatment administration. Appropriate safety assessments (e.g., evaluation of AEs and SAEs) should be repeated after dosing with study treatment. A physical examination, including general appearance and vital signs, will be performed as indicated in Table-2. If indicated, based on medical history and/or symptoms, additional exams will be performed at the discretion of the investigator. If possible, the same member of the study site staff throughout the study will perform assessments for an individual subject. Information for all physical examinations will be included in the source documentation at the study site. Significant findings that are present prior to the subject signing informed consent will be included in the Medical History. Significant findings made after the signing of the informed consent, which meet the definition of an AE, must be recorded as an AE. Vital signs (blood pressure, pulse, height, weight) will be assessed at each physical examination as indicated in Table-2 (see Supplemental 2 for details on how to acquire vital signs). Whether action needs to be taken to address notable vital signs will be decided by the investigator, considering the overall status of the subject. Laboratory studies will be drawn as indicated in Table-2. Whether action needs to be taken to address notable laboratory values will be decided by the investigator, considering the overall status of the subject. Hematology assessments will be measured at all scheduled study visits specified in Table-2. Serum chemistry will be a comprehensive metabolic panel will be measured at all scheduled study visits specified in Table-2.

If the prohibited treatment is being used during the study for any indication, the subject must discontinue use of the prohibited treatment if he/she wishes to continue in the study. In case of undue safety risk for the subject, the subject should discontinue study treatment at the discretion of the investigator/qualified site staff. If the subject received a live virus vaccination during the study, the subject must discontinue study treatment.

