### **3 Study Design**

#### **3.1 General Description**

This is a single center, exploratory, open-label, single-arm design study of 12 patients. Treatment naïve and treatment refractory patients with NL will be treated with ruxolitinib cream. Patients who are non-responders, to physician choice standard of care, such as topical, intralesional, and systemic or various non-steroidal including methotrexate, tumor necrosis factor alpha inhibitors, mycophenolate mofetil and fumaric acid esters will undergo a washout period and will be enrolled in the study.

Multiple safety studies have been conducted with ruxolitinib cream (see Safety) and a treatment regimen of 1.5% ruxolitinib cream BID on up to 20% BSA is deemed safe (Investigator's Brochure). Due to the thinned skin and potential for ulceration of NL, we will only treat up to 10% BSA Therefore, we propose a single center, exploratory, open-label, single-arm design study of 12 patients. Treatment naïve and treatment refractory patients with NL will be treated with ruxolitinib cream.

Individuals with NL will be eligible. All lesions will be treated, annotated, photographed, and scored. Prior treatment will be allowed; however, a washout period of 2 weeks for topical and 4 weeks for systemic agents which may alter disease course is required. At the washout period, individuals will undergo evaluation with a PGA, BSA calculation and NL lesion score lesion. Additional Pruritus measures using the NRS and Skindex-16 will be collected at that time.

Individuals will then initiate treatment on all lesions of NL BID and will be evaluated weekly and assessed by PGA, BSA, NL lesion score, Pruritus NRS, and Skindex-16 between weeks 0-4 (see Appendix). At week 12 will be the primary endpoint; however therapy will be continued for an additional 4 weeks. Therapy will be stopped and the individuals will be evaluated at week 12 and assessed by PGA, BSA, NL lesion score, Pruritus NRS, and Skindex-16. Laboratory and safety monitoring will occur at weeks 1, 2, 3, 4, 8, 12, 16. 3D photographs will be taken at weeks 0, 1, 2, 3, 4, 8, 12, 16. Individual lesions will be circled at that time and the exact volume of each lesion will be measured through use of 3D images. Up close photos will be taken of the disease and normal tissues attained at weeks 0 & 12.

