### NL Lesion Score:

Score 0-12

Erythema (0, none; 1, slight; 2, moderate; 3, severe)

Infiltration(0, none; 1, slight; 2, moderate; 3, severe)

Ulceration (0, none; 1, slight; 2, moderate; 3, severe)

Pain (0, none; 1, slight; 2, moderate; 3, severe).

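### Lesion outlines and 3D lesion volume are read with no masking to visit, although the images already planned could be read in random order with visit labels hidden

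*Combined protocol and SAP*

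**What the plan says.** Section 3.1 sets the design: "This is a single center, exploratory, open-label, single-arm design study of 12 patients". It schedules 3D photographs at weeks 0, 1, 2, 3, 4, 8, 12 and 16 and continues: "Individual lesions will be circled at that time and the exact volume of each lesion will be measured through use of 3D images". Table-2 has a photography row for the same eight time points, separate from the row for the clinical assessments.

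Section 3.5 lists change in lesional volume as a secondary endpoint, over seven contrasts among weeks 0, 4, 8, 12 and 16. The primary endpoint in Section 3.4 is a different measure: "Change in NL score (0-12) of the index treatment lesions (weeks 0 and 12". It is the bedside score in the appendix (Section 14), with four items graded 0 to 3: erythema, infiltration, ulceration and pain.

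On who assesses, the only rule is in the safety text of Section 3.6, which says that, where possible, "the same member of the study site staff throughout the study will perform assessments for an individual subject". It follows the sentences on physical examination and is repeated in Section 8.1 in the same setting. No section mentions a masked, independent or order-blind reader for any outcome.

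**The concern.** Volume from a 3D image looks like the most objective efficacy measure in this study, but it depends on where the lesion boundary is drawn. NL is an inflammatory plaque disease, and judgement enters at the edge. As written, lesions are circled at the imaging visit, when the week is known and everyone is known to be on active drug. A reader who expects shrinkage may draw a slightly tighter boundary later in treatment.

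In a two-arm blinded trial such a tendency would largely cancel. In a single-arm before-and-after comparison it adds to the estimated change, in the same direction as time on drug. Neither the paired Wilcoxon test nor the mixed model in Section 7.2 can remove it. Sections 7.1 and 7.2 intend the study to supply effect sizes for planning later trials, and a systematic shift would pass straight into them.

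**Working it through.** The documents contain no figure for reader bias, for the SD of lesional volume, or for a significance level, so there is no stated figure to reproduce. The check is a reading of the text, a count of the work, and one illustration of scale.

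**1. What the text establishes**
- Outlining: circled at the time of imaging (Section 3.1). The person is not named, and the text does not say whether the circle is made on the skin or on the image.
- Volume: measured from the images (Section 3.1). Reader, timing and labelling are not stated.
- Masking: none is described anywhere. For image reading this is an omission, not a stated unmasked procedure.

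**2. Reading load if labels are hidden**
- All scheduled images: 12 subjects × 8 time points = 96 image sets.
- Only the time points used in the Section 3.5 volume contrasts (weeks 0, 4, 8, 12, 16): 12 × 5 = 60.
- Day 0 and Week 12 only: 12 × 2 = 24.

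A set may hold several lesions, because all lesions are photographed. The number of outlines is therefore larger, by a factor that the documents do not give.

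**3. How much of the primary score images could support**
- Visible on a photograph: "Erythema (0, none; 1, slight; 2, moderate; 3, severe" and ulceration on the same scale, so 2 × 3 = 6 of 12 points.
- Not visible: "Pain (0, none; 1, slight; 2, moderate; 3, severe".
- Probably not gradable from an image: "Infiltration(0, none; 1, slight; 2, moderate; 3, severe".
- The PGA is graded as change from baseline, so its rater must know which state is baseline. It cannot be masked to visit as defined.

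**4. Scale, as illustration only**
The half-width of a 95% confidence interval for a mean change is t(0.975, 11) × SD / √12 = 2.201 × SD / 3.464 = 0.64 SD. An assumed reader shift of 0.25 SD would move the estimate by 0.25 / 0.64 = 39% of that half-width, and a shift of 0.5 SD by 0.5 / 0.64 = 78%. The interval would not reveal the shift. Both shifts are assumptions; nothing in the documents says that either occurs.

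**The case against.** The best case against the point is that the study declares itself open-label, exploratory and for estimation only, acknowledges that the NL score is unvalidated, and adds other measures. On this view, masked reading is a preference that would deliver less than it promises. Several parts of this stand:

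- **Masking would be partial.** Section 3.1 takes a lesional biopsy at Day 0 and another at Week 4, ideally from the same lesion. A visible biopsy site could reveal visit order, notably for Day 0 against Week 12. Staff at one site with 12 subjects may also recall a lesion's course.
- **Images may be missing.** Section 6 allows virtual visits for travelling patients.
- **There is some work.** Outlines made at the visit would have to be deferred or redone, and someone other than the reader must hold the key.
- **The primary endpoint stays unmasked.**

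A reader might also infer from Section 3.6 that one bedside assessor draws every outline knowing the visit. The text does not support that. The rule is qualified, sits among the physical-examination text, and mentions neither lesion outlining nor volume. Table-2 also separates photography from the clinical assessments.

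What does not stand is the appeal to estimation. Bias matters at least as much to an estimate as to a test, and declaring the design open-label does not prevent masking the reading of stored images.

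**Conclusion.** The point holds in a limited form and is minor. The plan leaves the reader, the timing and the masking of 3D lesion outlining and volume unspecified. In an open-label single-arm study, knowledge of the visit can therefore bias change in lesional volume in the same direction as time on drug. The size of that bias is unknown. A less exposed method is available with images and measurement work already planned, on at most 96 image sets.

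Two stronger readings are tempting and should not be drawn. The first is that a masked volume would be free of expectation; for the reasons above it would be better protected, not free, and natural course and regression to the mean would remain. The second is that the trial has an inflated false-positive rate. Simulated signed-rank tests with n = 12 and no true change reject in about 11% of trials for a shift of 0.25 SD and about 32% for 0.5 SD. Those figures rest on an assumed shift and an assumed two-sided 5% level. The plan states no level or success rule, and the fix would not change the rate for the primary score. They are not evidence of a defect.

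The conclusion assumes that circling happens at each imaging visit, which is the natural reading of Section 3.1, and that no separate imaging manual specifies masked reading; none is cited.

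**What to change.** In Section 3.1, replace the sentence on circling and volume with a short reading procedure:

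- After each subject's Week 16 visit, the staff who already measure the 3D images outline the lesions and compute volume in one batch and in random order.
- Another existing team member first strips visit and date from the files, sets the order and holds the key until the volumes are recorded.
- Any circle made at the visit serves only to identify the lesion, not as the measured boundary.
- The report states how many scheduled images are missing because of virtual visits, and that biopsy sites may have been visible.

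Keep the bedside NL score as primary. Optionally, re-score erythema and ulceration from the masked Day 0 and Week 12 files (24 sets) as a supportive analysis, stating that this covers 6 of the 12 points.

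The cost is a relabelling step, outlines deferred or redone on at most 96 image sets, and volumes that become available later. No extra reader, visit, procedure or subject is needed. That this effort is small is a judgement; the documents do not discuss reading cost.

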### 3.7 Identification of Source Data

All data in the study will be captured in the case report forms including:

- Safety measures
- Efficacy measures
- Laboratory studies
- Vital Signs
- Exploratory measures

## 4 Subject Selection Enrollment and Withdrawal

### 4.1 Inclusion Criteria

Subjects eligible for inclusion in this study must fulfill all the following criteria:

- Subjects must be able to understand and comply with the requirements of the study and communicate with the investigator. Subjects must give written, signed, and dated informed consent before any study related activity is performed. When appropriate, a legal representative will sign the informed consent according to local laws and regulation
- Both men and women must be at least 18 years of age at the time of screening
- Subjects must have clinical and histological features of NL
- Subjects must have at least one NL lesion measuring at least 1.7 cm
- NL must not affect greater than 10% BSA

## 4.2 Exclusion Criteria

Subjects fulfilling any of the following criteria are not eligible for inclusion in this study. To ensure the recruitment of a representative sample of all eligible subjects, the investigator may apply no additional exclusions.

- On excluded therapies, not on a stable dose of a therapy, or incompletely washed out for a therapy (Table-1).
- Known hypersensitivity to Ruxolitinib formulation.
- Pregnant or nursing (lactating) women (pregnancy is defined as the state of a female after conception and until the termination of gestation, confirmed by a positive human chorionic gonadotropin (hCG) laboratory test).
- Women of childbearing potential [Post-menopausal or not of child-bearing potential is defined by: 1 year of natural (spontaneous) amenorrhea or Surgical bilateral oophorectomy (with or without hysterectomy), total hysterectomy or tubal ligation at least 6 weeks ago. Oophorectomy alone must be confirmed by follow up hormone level assessment to be considered not of child-bearing potential, defined as all women physiologically capable of becoming pregnant, unless they are using medically acceptable methods of contraception which includes:
  - - Total abstinence (periodic abstinence and withdrawal are not acceptable methods of contraception).
    - Female sterilization (bilateral oophorectomy with or without hysterectomy), total hysterectomy, or tubal ligation at least 6 weeks before taking study treatment. Oophorectomy alone requires follow up hormone level assessment for fertility.
    - Male sterilization (at least 6 months prior to screening). The vasectomized male partner should be the sole partner for that subject.
    - Barrier methods of contraception: condom or occlusive cap.
    - Use of oral, injected or implanted hormonal methods of contraception or other forms or hormonal contraception that have complete efficacy (failure <1%). (The dose of the contraceptive should be stable for 3 months).
- Active ongoing inflammatory diseases of the skin other than NL that might confound the evaluation of the benefit of ruxolitinib cream.
- Underlying condition (including, but not limited to metabolic, hematologic, renal, hepatic, pulmonary, neurologic, endocrine, cardiac, infectious or gastrointestinal conditions) which, in the opinion of the investigator, significantly immunocompromised the subject and/or places the subject at unacceptable risk for receiving an immunomodulatory therapy.
- Active systemic infections during the 2 weeks prior to initiating trial medication (common cold viruses not included) or any infection that reoccurs on a regular basis.
- Current severe progressive or uncontrolled disease which the investigator renders the subject unsuitable for the trial or puts the subject at increased risk.

### 4.3 Subject Recruitment, Enrollment and Screening

- From the Principal Investigator or Co-Investigator clinical practices
- Screening requirements or qualifying lab values
- Evaluation and documentation of inclusion/exclusion criteria

### 4.4 Early Withdrawal of Subjects

#### 4.4.1 When and How to Withdraw Subjects

- Subject safety issues
- Failure of subject to adhere to protocol requirements
- Disease progression
- Subject decision to withdraw from the study (withdrawal of consent)

Subjects who withdraw from the study for any reason will have their information recorded at the time of withdrawal. At the time of withdrawal, the subject will be considered at the final treatment date and will move into the treatment observation phase (4 weeks). Subjects will not be replaced. Follow up for subjects will continue to follow the normal follow up (Table-2)

#### 4.4.2 Data Collection and Follow-up for Withdrawn Subjects

[figure not shown]
At the time of withdrawal, the reason for withdrawal will be recorded in the CRF. Individuals who withdraw will go into the observation phase for 4 weeks. If a subject withdraws consent, attempts will be made to obtain permissions to collect follow up information.

## 5 Study Drug

### 5.1 Description

The chemical name of INCB018424 phosphate is [REDACTED] (Figure 1). INCB018424 phosphate has a molecular formula of [REDACTED] and a molecular weight of [REDACTED]

#### INCB018424 Phosphate Structural Formula

INCB018424 phosphate drug substance is a white to off-white to light pink powder. Ruxolitinib cream has been formulated in 5 strengths ( [REDACTED] [REDACTED] ) that are actively being investigated. All excipients in both the ruxolitinib and vehicle cream formulations are compendial grade or are approved for use in topical products.

Ruxolitinib cream is a topical formulation of an investigational product under development for the treatment of patients with psoriasis, alopecia areata, atopic dermatitis, and other potential autoimmune diseases of the skin. INCB018424 phosphate (ruxolitinib) is an inhibitor of the Janus kinase (JAK) family of protein tyrosine kinases. ruxolitinib inhibits Janus Associated Kinases (JAKs) JAK1 and JAK2 which mediate the signaling of a number of cytokines and growth factors that are important for hematopoiesis and immune function. JAK signaling involves recruitment of STATs (signal transducers and activators of transcription) to cytokine receptors, activation and subsequent localization of STATs to the nucleus leading to modulation of gene expression. Mitogenic and inflammatory cytokines are strongly implicated in the pathogenesis of psoriasis, alopecia areata, atopic dermatitis, and other potential autoimmune diseases of the skin. Inhibition of specific cytokine function using antibodies directed against the common p40 subunit of interleukin (IL)-12 and IL-23 has demonstrated proof-of-concept validating cytokine signaling as a therapeutic target for the treatment of psoriasis. For details regarding pharmacodynamics and pharmacokinetics, please see IB.

